#### **5.5.4 Treatment Compliance**

The subject must return the bottle containing unused capsules (if any) to the study site for a compliance check at the visits specified in the SOA ([Appendix A, Table 2](#)).

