### 7.4. Exposure and Compliance

All subjects were expected to receive treatment twice daily for 14 consecutive days for a total of 28 doses. Total number of doses taken, number of missed doses, and compliance (%) will be summarized and listed for the Safety Population. Compliance via capsule count is defined in Section 6.1.8 as the rate of actual number of doses taken compared to the intended number of doses taken during the 2-week treatment period. Treatment compliance (rounded to the whole number) will also be categorized as <70%, ≥70 to 79%, ≥80 to 89%, ≥90% to 100%, and >100%.

Commercially Confidential Information

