Note: Percentages are n/Number of subjects in the Safety Population\*100.

Medical histories were coded using MedDRA version 21.1.

Subjects were counted once for each SOC and once for each PT.

Medical history terms are displayed by alphabetical order of SOC, then by decreasing frequency of PT within SOC, and then alphabetically by PT.

SOURCE: Listing 16.2.4.2

**Programming note:** ATC & PT text should be in title case in table, as shown in the shell. Ensure proper MedDRA version is printed in footnote.

Commercially Confidential Information

Commercially Confidential Information

Table 14.1.5.1  
Summary of Treatment Exposure and Compliance via Capsule Count  
Safety Population

Variable Statistic	Cohort-1 (N=XX)	Cohort-2 (N=XX)	Overall (N=XX)
Number of Doses Taken			
n	XX	XX	XX
Mean (SD)	XX.X (XX.X)	XX.X (XX.X)	XX.X (XX.X)
Median	XX.X	XX.X	XX.X
Min, Max	XX, XX	XX, XX	XX, XX
Number of Missed Doses			
n	XX	XX	XX
Mean (SD)	XX.X (XX.X)	XX.X (XX.X)	XX.X (XX.X)
Median	XX.X	XX.X	XX.X
Min, Max	XX, XX	XX, XX	XX, XX
Compliance (%)			
n	XX	XX	XX
Mean (SD)	XX.X (XX.X)	XX.X (XX.X)	XX.X (XX.X)
Median	XX.X	XX.X	XX.X
Min, Max	XX, XX	XX, XX	XX, XX
Compliance Category			
< 70%	XX (XX.X%)	XX (XX.X%)	XX (XX.X%)
≥ 70% to 79%	XX (XX.X%)	XX (XX.X%)	XX (XX.X%)
≥ 80% to 89%	XX (XX.X%)	XX (XX.X%)	XX (XX.X%)
≥ 90% to 100%	XX (XX.X%)	XX (XX.X%)	XX (XX.X%)
> 100%	XX (XX.X%)	XX (XX.X%)	XX (XX.X%)

Note: Percentages are n/Number of subjects in the Safety Population\*100. Subjects were to receive treatment twice daily for 14 consecutive days for a total of 28 doses. Compliance is number of doses taken / number of expected doses \* 100%. Number of doses taken is calculated as the number of expected doses (number of capsules dispensed) minus total number of pills not taken minus number of unused capsules returned, as collected in the case report form. Expected doses are summed up to the point of discontinuation (eg, if a subject discontinues early, only planned doses up to that discontinuation day are counted in the denominator).

SOURCE: Listings 16.2.5.1, 16.2.5.2, and 16.2.5.3

Table 14.1.5.2

Commercially Confidential Information

Table 14.2.1.1.1  
Summary of Central Rater TETRAS-PS Scores by Study Visit  
FAS and Per-Protocol Population

Parameter: TETRAS-PS Total Score

Study Visit Statistic	Full Analysis Set			Per-Protocol Population		
	Cohort-1 (N=XX)	Cohort-2 (N=XX)	Overall (N=XX)	Cohort-1 (N=XX)	Cohort-2 (N=XX)	Overall (N=XX)

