**Programming note:** Concatenate specify text for Treatment Type, Trigger Type, Frequency Type as shown above if the answer is "OTHER"

Listing 16.2.5.1  
Study Drug Administration  
All Subjects

Subject ID	Protocol Amendment	Study Visit	Administered Proper Dosage of Study Drug?	Reason Dose Not Administered	Date/Time of In-Clinic Administration (Study Day)	Date/Time of Last Dose Prior to Clinic Visit (Study Day)
XXXXXX	X.X	XXXXXXX	Yes	XXXXXXXXXXXXXXXXXX	DDMMYY/HH:MM	DDMMYY/HH:MM
	X.X	XXXXXXX	Yes		DDMMYY/HH:MM	DDMMYY/HH:MM
	X.X	XXXXXXX	Yes		DDMMYY/HH:MM	DDMMYY/HH:MM
	X.X	XXXXXXX	Yes		DDMMYY/HH:MM	DDMMYY/HH:MM
		XXXXXXX	No			
XXXXXX	X.X	XXXXXXX	Yes	XXXXXXXXXXXXXXXXXX	DDMMYY/HH:MM	DDMMYY/HH:MM
	X.X	XXXXXXX	Yes		DDMMYY/HH:MM	DDMMYY/HH:MM
	X.X	XXXXXXX	Yes		DDMMYY/HH:MM	DDMMYY/HH:MM

Note: Study day is calculated relative to the date of first dose of study drug.  
Time for last dose prior to clinic visit is approximate.

Listing 16.2.5.2  
Drug Accountability  
All Subjects

Subject ID	Protocol Amendment	Total Daily Dose	Bottle	Date Dispensed (Study Day)	Number of Capsules Dispensed	Was Bottle Returned to the Clinic?	Date Returned (Study Day)	Number of Unused Capsules Returned
XXXXXX	X.X	300 mg BID	Bottle A	DDMMYYYY (X)	XX	Yes	DDMMYYYY (X)	XX
XXXXXX	X.X	300 mg BID	Bottle A	DDMMYYYY (X)	XX	Yes	DDMMYYYY (X)	XX

Note: Study day is calculated relative to the date of first dose of study drug.

**Programming note:** Concatenate specify text with a colon if the Capsules Dispensed is OTHER.

Listing 16.2.5.3  
Missed Doses  
All Subjects

Subject ID	Protocol Amendment	Were any Doses Missed?	Date of Missed Dose (Study Day)	AM/PM Dose	Number of Pills not Taken	Reason for Missed Dose
XXXXXX	X.X	No				
XXXXXX	X.X	Yes	DDMMYYYY (X)	AM	XX	XXXXXXXXXXXX
XXXXXX	X.X	Yes	DDMMYYYY (X)	PM	XX	XXXXXXXXXXXX

Note: Study day is calculated relative to the date of first dose of study drug (= Date of Missed Dose – first dose date + 1).

Commercially Confidential Information

Commercially Confidential Information

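### The Table 14.1.5.1 note deducts a missed-and-returned capsule twice, against SAP 6.1.8, and 6.1.8 itself gives expected doses two values

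*SAP*

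**What the plan says.** SAP 7.4 plans a Safety Population summary of doses taken, doses missed and compliance, against 28 planned doses. It states that "Compliance via capsule count is defined in Section 6.1.8". It adds that "Treatment compliance (rounded to the whole number) will also be categorized", using five rows that run from below 70% to above 100%.

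SAP 6.1.8 defines compliance as capsules taken divided by expected doses. For completers, expected doses is the sum of clinic capsules and capsules dispensed for home use. That sum is set equal to the days from the Day 1 visit to the Day 14 visit, inclusive, times 6. Capsules taken is expected doses less lost capsules less returned capsules. For a completer treated longer (its example is 15 days), expected doses stays at 84 and compliance is predicted to exceed 100%.

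The note under Table 14.1.5.1 (SAP 14.2) gives a different numerator. It starts from the "number of expected doses (number of capsules dispensed", where the bracket is the note's own gloss, and continues "minus total number of pills not taken minus number of unused capsules returned". The table's source line is "SOURCE: Listings 16.2.5.1, 16.2.5.2, and 16.2.5.3". Listing 16.2.5.2 (Drug Accountability) has a column "Number of Unused Capsules Returned". Listing 16.2.5.3 (Missed Doses) has a column "Number of Pills not Taken".

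Protocol 5.5.4 requires the return of leftover drug: "The subject must return the bottle containing unused capsules (if any) to the study site for a compliance check".

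**The concern.** A missed capsule should ordinarily come back in the bottle. It is then recorded once as missed and once as returned, and the note subtracts both records. Nothing in the SAP limits the missed-pill count to capsules that were not returned.

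The note also disagrees with 6.1.8 in two other ways. It has no term for lost capsules, and it equates expected doses with capsules dispensed, whereas 6.1.8 adds capsules taken at the clinic. A programmer working from the shell and a validator working from 6.1.8 would get different numbers.

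Within 6.1.8, the same term starts the numerator and forms the denominator, but the text gives it two values when treatment runs long.

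The study's primary objective is safety and tolerability over 14 days of dosing, and this table reports how much drug subjects took. Followed as written, the note understates that for subjects who return logged missed capsules.

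**Working it through.** **Inputs.** 28 planned doses (SAP 7.4); 3 capsules per dose (protocol 5.5.3); 6 capsules per day and the compliance formula (SAP 6.1.8); whole-percent rounding and the rows (SAP 7.4). The documents give no missed-dose rate, so the results below are illustrations for single subjects.

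**The plan's own figure.** 14 days × 6 = 84, and 28 doses × 3 = 84. The 84 reproduces.

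**Double deduction.** Take a 14-day completer with m missed doses, all logged, all 3m capsules returned and none lost.

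- Each untaken capsule deducted once (also the 6.1.8 result): (84 − 3m)/84.
- Table note: (84 − 3m − 3m)/84.
- Difference: 3/84 = 3.57 points per missed dose.

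| m | Deducted once | Table note | Row (once → note) |
|---|---|---|---|
| 1 | 81/84 = 96.4% | 78/84 = 92.9% | 90–100 (same) |
| 2 | 78/84 = 92.9% | 72/84 = 85.7% | 90–100 → 80–89 |
| 3 | 75/84 = 89.3% | 66/84 = 78.6% | 80–89 → 70–79 |
| 4 | 72/84 = 85.7% | 60/84 = 71.4% | 80–89 → 70–79 |
| 5 | 69/84 = 82.1% | 54/84 = 64.3% | 80–89 → below 70 |
| 6 | 66/84 = 78.6% | 48/84 = 57.1% | 70–79 → below 70 |
| 7 | 63/84 = 75.0% | 42/84 = 50.0% | 70–79 → below 70 |
| 8 | 60/84 = 71.4% | 36/84 = 42.9% | 70–79 → below 70 |

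From 9 missed doses on, both results are below 70% (57/84 = 67.9% at m = 9).

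**Internal check.** At m = 2 the note gives 72 capsules, or 24 doses taken. With 2 missed doses in the row beneath, the table accounts for 26 of the 28 doses that the same note states.

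**Partial return.** If r of the 3m missed capsules come back, the note gives (84 − 3m − r)/84. At m = 2:

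- r = 0: 78/84 = 92.9% (no error)
- r = 2: 76/84 = 90.5% (row unchanged)
- r = 3: 75/84 = 89.3%, which rounds to 89% (one row down)
- r = 6: 72/84 = 85.7%

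**Opposite direction.** With 3 capsules lost and no missed dose recorded, 6.1.8 gives 81/84 = 96.4% and the note gives 100%.

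**15-day completer, nothing lost or returned.** The date formula gives 15 × 6 = 90; the specific rule gives 84.

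- 84 in both places: 84/84 = 100%.
- 90 in both places: 90/90 = 100%.
- Supply above, 84 below: 90/84 = 107.1%.

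Lost and returned counts cannot be negative, so any single value used in both places caps compliance at 100%. Only the third line gives the result that 6.1.8 predicts.

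**The case against.** The best reply is that a governing definition exists. Section 7.4 points to 6.1.8, and 6.1.8 does not count a missed capsule twice. The double deduction sits in a table note and does harm only if that note is programmed. This stands, and it keeps the severity low. It does not remove the conflict, because the note is an explicit instruction attached to the table it describes.

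A second reply is that citing both listings as sources proves nothing, since the table has its own row for missed doses and needs Listing 16.2.5.3 anyway. That is right. The finding rests on the wording of the note, not on the source line.

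A reader might infer from 6.1.8 that the row above 100% can never be filled. The documents do not support that. Section 6.1.8 also equates expected doses with supply, and the note starts from capsules dispensed, so 90/84 can be reached. The general formula followed by an 84 rule for longer treatment can be read as a rule with an exception. What remains is one term carrying two values.

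A reader might also infer that subjects would drop out of an analysis population, because protocol 11.1 sets at least 90% compliance for the Exposed Population. The corresponding SAP text is blacked out, so it cannot be shown which compliance figure would apply.

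Finally, simply deleting the missed-pill term can err the other way. A completer with two logged missed doses who returns nothing and reports no loss would show 84/84 = 100% instead of 78/84 = 92.9%. The 6.1.8 rule for unreturned capsules covers only subjects who discontinued. This objection stands, and the fix allows for it.

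**Conclusion.** The point holds, at low severity. As written, the note deducts a missed-and-returned capsule twice and contradicts the definition that Section 7.4 names. The error is 3.6 points per missed dose when all missed capsules are logged and returned. It shrinks in proportion to the share returned and is zero when none are returned. One missed dose changes no row; 2 to 8 fully returned missed doses move a subject down at least one row.

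Section 6.1.8 needs a separate clarification: expected doses means supply in one place and 84 in another, and its predicted over-100% result depends on using one above the line and the other below.

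These results assume a 14-day completer with 84 scheduled capsules, except in the 15-day case. No claim is made for 13-day completers. How often the error would occur cannot be estimated from the documents. The table is descriptive, and no effect on treatment-emergent adverse event counts or on an analysis population is shown.

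**What to change.** Delete the missed-pill deduction from the Table 14.1.5.1 note and use one definition in the note and in 6.1.8:

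- **Capsules taken** = capsules taken at the clinic (if not drawn from the home supply) + capsules dispensed for home use − returned − lost − logged missed capsules that were neither returned nor reported lost. Each untaken capsule is then deducted once. With two missed doses this gives 78/84 = 92.9% whether all, some or none of the 6 capsules come back.
- **Denominator** = scheduled capsules, with 84 for longer treatment as 6.1.8 already states, prorated at discontinuation. Use a separate name for supply, so that expected doses has one meaning.
- **Doses** = capsules / 3, so that the dose rows are on the 28-dose scale.

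State whether the clinic doses come from the dispensed bottles. The documents do not say, and the Day 7 and Day 14 clinic doses alone are 6 capsules, or 6/84 = 7.1 points.

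The cost is text edits to 6.1.8 and one table note. Dispensed, returned and missed capsules are already listed. Section 6.1.8 says lost capsules are collected on the case report form, but Listing 16.2.5.2 has no column for them, so one may need to be added.

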***Continue for Days 7, 14, and 21 and all parameters.***

Abbreviations: TETRAS-PS = Tremor Research Group Essential Tremor Rating Assessment Scale (TETRAS)-performance subscale (PS).

Note: TETRAS-PS Total score is derived as the sum of all of the individual item scores, with the exception of item 5, only the maximum of the lower limb tremor scores will be counted. Each individual item question score ranges from 0 to 4, where higher scores indicate worse quality of life.

[1] Pearson correlation coefficient is presented for all study visits.

[2] P-value for testing the correlation is 0.

[3] The baseline value is the last observation recorded prior to the first dose of treatment.

SOURCE: Listings 16.2.6.1.1, 16.2.6.1.2

***Programming Note:*** Check Section 8.3.2 of SAP. If Spearman correlation coefficient is used, update footnote [1] accordingly.

Table 14.2.1.1.5  
Summary of Local Rater TETRAS-PS Scores by Study Visit  
FAS and Per-Protocol Population

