#### **8.2.1. TETRAS Performance Subscale Scores**

The TETRAS-PS Subscale (Version 3.1) score includes the following 9 items: head tremor, face (including jaw) tremor, voice tremor, upper limb tremor (left/right), lower limb tremor, Archimedes spirals, handwriting, dot approximation task, and standing tremor. Scores for each item range from 0 to 4 in increments of 0.5. Derivation for the TETRAS-PS Total score is described in Section 6.1.8. For lower limb tremor, only the maximum of the item 5 scores will be used. The TETRAS-PS assessments will be administered by a certified rater (referred to as a local rater hereafter) at Screening, Pre-dose, Day 1, Day 7, Day 14, and Day 21. The TETRAS-PS assessments will also be recorded using videography for centralized evaluation and rating by independent blinded central raters (neurologists) with expertise in the assessment of ET. All scores (item scores and total scores) by both local and central raters will be analyzed in the same way as described below for central rater data.

Observed values and change from baseline in each item score and in TETRAS-PS total score by central rater will be summarized overall, by cohort (see Section 6.1.2), and by study visit using descriptive statistics.

Additionally, tests of hypotheses comparing mean and median TETRAS-PS total scores between baseline and subsequent study visits will be conducted using a 2-sided paired t-test or Wilcoxon signed rank test. The null hypothesis is that the change from baseline in TETRAS-PS total score to subsequent visit is 0 with a 2-sided alternative considering a difference not 0 (significant changes in tremor).

As a supportive analysis, change from Screening to Baseline and change from Day 14 to Day 21 in each item score and in TETRAS-PS total score will be summarized overall and by cohort (see Section 6.1.2) using descriptive statistics.

Commercially Confidential Information

Commercially Confidential Information

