## **10. Changes from the Protocol-Planned Analysis**

TETRAS scores from both the central rater and local raters will be summarized. all rating scores will be listed.

Commercially Confidential Information

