**Programming note:** Continue for Cohort-2 and Overall. Items include: Head Tremor, Face (including jaw) Tremor, Voice Tremor, Upper Limb Tremor: Forward Outstretched Postural Tremor-Right, Upper Limb Tremor: Forward Outstretched Postural Tremor-Left, Upper Limb Tremor: Lateral Wing Beating Postural Tremor-Right, Upper Limb Tremor: Lateral Wing Beating Postural Tremor-Left, Upper Limb Tremor: Kinetic Tremor-Right, Upper Limb Tremor: Kinetic Tremor-Left, Lower Limb Tremor: Extended-Right, Lower Limb Tremor: Extended-Left, Lower Limb Tremor: Heel-Shin-Right, Lower Limb Tremor: Heel-Shin-Left, Archimedes Spirals-Right, Archimedes Spirals-Left, Handwriting, Dot Approximation Task-Right, Dot Approximation Task-Left, and Standing Tremor.

Table 14.2.1.1.4

Correlation between Central and Local TETRAS-PS Scores by Study Visit  
FAS and Per-Protocol Population

Parameter: TETRAS-PS Total Score		Full Analysis Set			Per-Protocol Population		
Study Visit Statistic	Cohort-1 (N=XX)	Cohort-2		Overall (N=XX)	Cohort-2		Overall (N=XX)
		Cohort-1 (N=XX)	Cohort-2 (N=XX)		Cohort-1 (N=XX)	Cohort-2 (N=XX)	
Screening							
Correlation [1]	X.XXXX	X.XXXX	X.XXXX	X.XXXX	X.XXXX	X.XXXX	X.XXXX
P-Value [2]	X.XXXX	X.XXXX	X.XXXX	X.XXXX	X.XXXX	X.XXXX	X.XXXX
Baseline [3]							
Correlation	X.XXXX	X.XXXX	X.XXXX	X.XXXX	X.XXXX	X.XXXX	X.XXXX
P-Value	X.XXXX	X.XXXX	X.XXXX	X.XXXX	X.XXXX	X.XXXX	X.XXXX
Day 1, Post-dose							
Correlation	X.XXXX	X.XXXX	X.XXXX	X.XXXX	X.XXXX	X.XXXX	X.XXXX
P-Value	X.XXXX	X.XXXX	X.XXXX	X.XXXX	X.XXXX	X.XXXX	X.XXXX

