**Same shell as Table 14.2.1.1.1**

**Programming Note:** Continue for all parameters. Parameters include: Head Tremor, Face (including jaw) Tremor, Voice Tremor, Upper Limb Tremor: Forward Outstretched Postural Tremor-Right, Upper Limb Tremor: Forward Outstretched Postural Tremor-Left, Upper Limb Tremor: Lateral Wing Beating Postural Tremor-Right, Upper Limb Tremor: Lateral Wing Beating Postural Tremor-Left, Upper Limb Tremor: Kinetic Tremor-Right, Upper Limb Tremor: Kinetic Tremor-Left, Lower Limb Tremor: Extended-Right, Lower Limb Tremor: Extended-Left, Lower Limb Tremor: Heel-Shin-Right, Lower Limb Tremor: Heel-Shin-Left, Archimedes Spirals-Right, Archimedes Spirals-Left, Handwriting, Dot Approximation Task-Right, Dot Approximation Task-Left, and Standing Tremor. Change from Screening should only be presented after the baseline visit.

Table 14.2.1.2.1  
Summary of Central Rater TETRAS-PS Upper Limb Subscale Scores by Study Visit  
FAS and Per-Protocol Population

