#### **14.4. Planned Figure Shells**

Commercially Confidential Information

Figure 14.2.1.1.4  
Central and Local TETRAS-PS Total Scores by Study Visit  
Full Analysis Set

Abbreviation: TETRAS-PS = Tremor Research Group Essential Tremor Rating Assessment Scale (TETRAS)-performance subscale (PS).

Note: TETRAS-PS Total score is derived as the sum of all of the individual item scores. Each individual item question score ranges from 0 to 4, where higher scores indicate worse quality of life. Pearson correlation coefficient and regression lines are presented for all study visits.

Reference Table: 14.2.1.1.4

SOURCE: Listings 16.2.6.1.1, 16.2.6.1.2

**Programming Note:** Check Section 8.3.2 of SAP. If Spearman correlation coefficient is used, update footnote [1] accordingly. A separate graph will be produced for each study visit.

Commercially Confidential Information

Figure 14.2.1.2.3  
Central and Local TETRAS-PS Upper Limb Subscale Scores by Study Visit  
Full Analysis Set

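### The only visible statistic pairing central with local TETRAS-PS scores is a correlation tested against 0, which does not move with a systematic rater shift; a paired difference with a 95% CI should be added

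*SAP*

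**What the plan says.** SAP 14.2 contains three tables that set central against local scores visit by visit. Table 14.2.1.1.4, titled "Correlation between Central and Local TETRAS-PS Scores by Study Visit", covers the total score. Tables 14.2.1.2.3 (upper limb subscale) and 14.2.1.3.2 (Item 4) reuse its shell. Each visit has two rows, a coefficient and a P value. The footnotes define them: "Pearson correlation coefficient is presented for all study visits" and "P-value for testing the correlation is 0". A programming note adds: "If Spearman correlation coefficient is used, update footnote [1] accordingly". That note refers to SAP Section 8.3.2, which cannot be seen in the public text.

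The companion figures in SAP 14.4 (14.2.1.1.4, 14.2.1.2.3 and 14.2.1.3.2) are drawn separately for each visit, and their footnote says: "Pearson correlation coefficient and regression lines are presented for all study visits".

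Each source is also analysed separately. SAP 8.2.1 states: "All scores (item scores and total scores) by both local and central raters will be analyzed in the same way". Sections 8.2.2 and 8.2.3 say the same for the subscale and Item 4, and Section 10 records: "TETRAS scores from both the central rater and local raters will be summarized". Local Table 14.2.1.1.5 carries the instruction "Same shell as Table 14.2.1.1.1". That central shell gives mean, SD, mean change from baseline, SE, 95% CI and P values by visit, for each cohort and overall. Tables 14.2.1.2.4 and 14.2.1.3.3 do the same for the other two local scores.

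The trial is open-label with one arm (SAP 3.5 and 3.6). Central raters are independent and blinded and work from video (Protocol 8.1, SAP 8.2.1).

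**The concern.** With no control arm and local raters who know that the subject is on drug, a natural use of the blinded video ratings is to ask whether local raters record more improvement than central raters. That is a question about a systematic difference. The one visible statistic that pairs the two ratings measures something else, namely whether subjects who score high with one rater also score high with the other. A correlation can be near 1 while local scores all sit several points below central scores.

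The P value adds little. Both raters score the same recorded performance, so zero correlation is not a serious hypothesis. The risk is one of reporting: a high r with a small P value could be taken as reassurance about rating bias, which it cannot give.

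**Working it through.** The documents state no agreement, power or precision figure for this comparison, so there is none to reproduce. The check has four steps.

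**1. Invariance.** Let c be the central score, l the local score and k a constant shift in the local score.

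- r(c, l + k) = cov(c, l + k) / (SD(c) × SD(l + k)) = cov(c, l) / (SD(c) × SD(l)) = r(c, l).
- Adding k leaves the ranks unchanged, so Spearman's coefficient is unchanged too.
- The mean difference moves by k.
- In a regression of c on l, the slope b is unchanged and the intercept moves by −b × k.

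One simulated sample of 30 (slope 0.666 throughout) shows this:

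| Local shift | Pearson r | Mean local − central | Intercept |
|---|---|---|---|
| 0 | 0.778346 | 0.279 | 10.193 |
| −4 | 0.778346 | −3.721 | 12.859 |
| −8 | 0.778346 | −7.721 | 15.524 |

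**2. What the test of zero correlation requires.** The two-sided 0.05 level comes from SAP 4.1 and the maximum of 30 subjects from SAP 3.2. The critical value is |r| = t / √(n − 2 + t²).

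- n = 30: t = 2.048, so 2.048 / √(28 + 4.195) = 0.361.
- n = 15: 0.514. n = 10: 0.632.

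Power by Fisher z is Φ(atanh(ρ) × √(n − 3) − 1.96). At n = 30 and ρ = 0.5 this is Φ(0.549 × 5.196 − 1.96) = 81%. For ρ of 0.7 or more it exceeds 99%. At n = 15 it is 48% for ρ = 0.5, 85% for 0.7 and 97% for 0.8.

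**3. Correlation against paired difference.** The inputs here are assumptions, since the documents give none: bivariate normal scores, SD 6 for both raters, n = 30, ρ = 0.8, and 2,000 simulated trials per row. Lin's concordance coefficient (CCC) is 2ρSD² / (2SD² + shift²); for a shift of −4 it is 57.6 / (72 + 16) = 0.655.

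| Shift | Mean r | r significant | CCC (theory) | Paired test rejects |
|---|---|---|---|---|
| 0 | 0.795 | 100% | 0.800 | 5% |
| −2 | 0.796 | 100% | 0.758 | 79% |
| −4 | 0.795 | 100% | 0.655 | 100% |
| −6 | 0.794 | 100% | 0.533 | 100% |

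With ρ from 0.7 to 0.9, the paired test detects a −2 point shift in 65% to 98% of trials.

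The precision available is useful. The SD of the difference is 6 × √(2 × (1 − 0.8)) = 3.79, so the 95% CI half-width is 2.045 × 3.79 / √30 = 1.42 points. At ρ = 0.7 (SD 4.65) it is 1.74, and at ρ = 0.9 (SD 2.68) it is 1.00. These are for scores at one visit; the SD for a difference in change may differ.

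**4. Whether the reader can recover the paired estimate from the planned outputs.** If the same subjects appear in both tables, subtracting the two means gives the mean paired difference exactly. For scores at one visit, the variance s_l² + s_c² − 2 r s_l s_c could even be assembled by hand when Pearson r is reported. For change from baseline it could not, because that needs the correlation between local and central changes, and the shells give only correlations of scores. The subject sets may also differ: Listing 16.2.6.1.1 tracks whether each video was uploaded, and SAP 6.1.8 allows no imputation of missing items.

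**The case against.** The strongest reply is that a shift would not go unseen. The central and local tables carry the same change-from-baseline summaries, so local changes that were 5 points more favourable would show as a 5-point gap between the two means. The regression plots would show it as well. This stands. A reader might infer that agreement is judged only by Pearson's r, or that the plan is blind to a rater shift. The documents support neither reading: Spearman is allowed, and the parallel tables and plots exist. What they lack is a paired estimate with a CI.

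Purpose is the second point. The visible SAP titles these tables as correlations. It does not call them an agreement analysis or a check on open-label bias, and it does not say that a high r is reassuring. A reader might infer that the sponsor intends that use, but it is not written. That the comparison ought to address bias is a judgement from the design.

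Third, parts of SAP 8.2, Section 10 and the planned-table list in 13.2 are blacked out, and Section 8.3.2 is not visible. An agreement method could sit there, so the point is limited to what can be seen.

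Fourth, it would be too strong to say that the test of zero correlation always rejects. The tables also run by cohort, cohort sizes are not given, and single items scored 0 to 4 may correlate weakly.

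**Conclusion.** The point holds in a limited form. Among visible outputs, the only statistic that pairs central with local scores is a Pearson or Spearman correlation tested against 0, and it is unaffected by a constant shift between raters. That follows from algebra and needs no assumption. The separate tables and plots show a mean shift descriptively, without a paired estimate or a CI. The detection rates and CI widths rest on an assumed SD of 6, correlations of 0.7 to 0.9 and 30 subjects with both ratings, and are illustrations only.

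The consequence is small. The primary endpoint is safety, TETRAS-PS is secondary, and the blinded central scores are summarised and tested in their own right, so no efficacy conclusion depends on the correlation. This is a cheap improvement, not a defect that threatens the trial's reading.

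**What to change.** In Tables 14.2.1.1.4, 14.2.1.2.3 and 14.2.1.3.2, among subjects with both ratings at the visits concerned, add n and the mean paired difference (local minus central) with a 95% CI:

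- in score at every visit, including Screening and Baseline, which shows any gap between live and video rating before dosing;
- in change from baseline at Days 1, 7, 14 and 21, where a constant gap cancels and a shift arising after dosing remains. This row does not apply at Screening or Baseline.

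Limits of agreement or an absolute-agreement intraclass correlation may accompany it. State in the SAP that r and its P value will not be presented as evidence of agreement or of absence of open-label rating bias. Dropping the test of zero correlation is optional.

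The cost is one extra paired summary per table, from data already collected.
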